4. STATISTICAL METHODS

4.1. General Statistical Considerations

The analyses will be performed using SAS® software (version 9.1 or subsequent, SAS Institute, North Carolina USA).

The descriptive analysis of qualitative and ordinal variables will include numbers and frequency of each modality together with its 95% confidence interval and the number of missing data. Quantitative variables will be described as numbers, mean and median values, standard deviation, confidence interval and the number of missing data.

Overall survival and progression-free survival data will be described by Kaplan Meier curves. Median survival will be estimated and presented with its 95% CI.

Wherever possible, a graphical representation will be combined with results of the analyses.

Association measurements between two variables (univariate analyses excluding comparison of subgroups of interest) will use standard methods. The association between the two qualitative variables will be measured by calculating the Chi squared Pearson coefficient. If validity is not met, the continuity correction will be used (Yates Chi squared coefficient)

provided it is logically possible to group modalities together. Mean values of quantitative variables will be compared using the Student test with and without the hypothesis that variances are equivalent. Equivalence of variances will be estimated using a Levène test and the definition of a normal distribution will be assessed from the appearance of histograms and result of the Shapiro-Wilk test.

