4.5. Handling of Missing Values

In general, missing values will not be used either in calculating the percentages or in computing statistical tests.

The number of missing values for each analysed variable will be shown in the summary tables. Key data will be mandatory in the electronic CRF in order to control the proportion of missing data.

Dates, only used to calculate time periods:

- For the data of birth, the day is not requested in the CRF and will be replaced by 15.
- For calculations involving dates:
 - If the day is missing, it will be replaced by day 15 of the month;
 - If the month and day are missing, they will be replaced by 30 June of the year;
 - If the date is completely missing, it will not be replaced.

These rules will be used if they do not create inconsistencies (negative time intervals). Otherwise the time interval will be deemed to be missing.

The other specific management requirements for missing data are described in the relevant sections of this document.

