4.7. Derived Variables

• Total duration of exposure to the documented treatment in the study (months)

(Date of last receipt of treatment – Date of first receipt of treatment + 1)/30.4375

For patients who drop out of the study early, the date of last receipt of the treatment considered will be the date of the last visit.

To analyse exposure times by treatment received at least once during the study, if the start date is after the date of the last visit, the treatment will not be considered.

In terms of exposure time for treatments used in combination, the start date and end date of the combination were not recorded in the CRF. The visit prior to the report describing addition of the combination will be deemed to be the start date and the visit in which the combination is reported as being discontinued will be deemed to be the end date for the combination, unless the combination began or finished during a line of treatment (or includes the start and end date).

• In general, the time between two dates expressed in days will be obtained as follows:

Most recent date – Least recent date

The following conversion factors will be used to convert the times into months or years:

- 1 month = 30.4375 days
- 1 year = 365.25 days
- Age (in years) will be calculated as follows:

(Inclusion date – Date of birth)/365.25

• The disease duration (in years) will be calculated as follows:

(Inclusion date – Disease start date)/365.25

• The disease duration (in years) at start of the current treatment at inclusion will be calculated as follows:

(Treatment start date - Diagnosis date) / 365.25

• Time until first temporary discontinuation since inclusion into the study:

(Date of first temporary discontinuation – Date of inclusion + 1)/30.4375

• Time until permanent treatment discontinuation since inclusion into the study:

(Date of final discontinuation – Date of inclusion + 1)/30.4375

• Lines of cancer treatment:

Treatment lines will be defined in two ways:

- Main treatment line: All new treatments will be considered as a new main treatment line.
- Main concomitant treatment line: All new treatments or new combinations will be deemed to be a new concomitant treatment line.

The reason for discontinuing treatment will not be considered in the definition of a treatment line.

The same treatment stopped for over 3 months will be deemed to be two different lines of treatment and to be one line if the discontinuation lasts for less than 3 months.

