5.7.1. Treatment Drop-outs and Documented Reasons for Dropping Out of the Study

The following parameters will be presented for each of the analysis groups (targeted therapy or other treatment) and for each treatment:

- Total duration of exposure since starting treatment (also shown for the reference set).
- Numbers and percentages of patients who had at least one documented discontinuation of treatment in the study. The results will be shown for incident patients, prevalent patients and then for all patients.
- Number of documented temporary discontinuations by patient in the study.

- Time to the first temporary discontinuation from inclusion into the study. The results will be shown for incident patients, prevalent patients and then for all patients.
- Reasons for temporary discontinuations.
- Durations of temporary discontinuations.
- Numbers and percentages of patients who discontinued treatment permanently.
- Time until permanent discontinuation from inclusion into the study. The results will be shown for incident patients, prevalent patients and then for all patients.
- Time until permanent discontinuation from inclusion. Results will be shown for incident patients, prevalent patients and then for all patients.
- Reason for permanent discontinuation.

The analyses of exposure to treatment will be described by treatment received at inclusion but also by treatment received at least once during the study (main treatment or as a combination). If the patient takes the same treatment on several occasions over different periods, the sum of the exposure periods will be calculated.

The analyses of temporary discontinuations will be described by main treatment received at inclusion but also by main treatment ongoing at the time of temporary discontinuation.

In addition, the total duration of exposure of the treatment at inclusion since it was started will be analysed by the ECOG index value at inclusion.

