Time to the first temporary discontinuation since inclusion	N	XX	NA	XX
(months)	Missing data	XX		XX
	Mean (SD)	XX.XX (X.XX)		XX.XX
	Median	XX.X		(X.XX) XX.X
	[Min; Max]	[XX.X; XX.X]		[XX.X; XX.X]
	[Q1; Q3]	[XX.X; XX.X]		[XX.X; XX.X]
Time to the first temporary discontinuation since inclusion (N(%))	N	XX	NA	XX
(4.(7.0))	Missing data]0-3] months]3-6] months > 6 months	XX XX (XX.X%) XX (XX.X%) XX (XX.X%)		XX XX (XX.X%) XX (XX.X%) XX (XX.X%)
Time to the first temporary discontinuation since inclusion	N	XX	NA	XX
(months) – incident patients	Missing data	XX	1112	XX
	Mean (SD)	XX.XX (X.XX)		XX.XX
	Median	XX.X		(X.XX) XX.X
	[Min; Max]	[XX.X; XX.X]		[XX.X; XX.X]
	[Q1; Q3]	[XX.X; XX.X]		[XX.X; XX.X]
Time to the first temporary discontinuation since inclusion	N	VV	NIA	-
(N(%)) – incident patients	N Missing data	XX	NA	XX
	Missing data]0-3] months]3-6] months > 6 months	XX XX (XX.X%) XX (XX.X%) XX (XX.X%)		XX XX (XX.X%) XX (XX.X%) XX (XX.X%)
Time to the first temporary discontinuation since inclusion (months) – prevalent patients	N	XX	NA	XX
(montas) - prevatent patients	Missing data	XX		XX
	2			

Table 14.3.1.5: Temporary Discontinuations of the Main Treatment at Inclusion Documented in the Study – Safety Analysis Set

		Targeted therapies (N=XX)	Other treatments (N=XX)	Total (N=XX)
	Mean (SD)	XX.XX (X.XX)		XX.XX (X.XX)
	Median	XX.X		XX.X
	[Min; Max]	[XX.X; XX.X]		[XX.X; XX.X]
	[Q1; Q3]	[XX.X; XX.X]		[XX.X; XX.X]
Time to the first temporary discontinuation since inclusion $(N(\%))$ – prevalent patients	N	XX	NA	XX
	Missing data [0-3] months [3-6] months > 6 months	XX XX (XX.X%) XX (XX.X%) XX (XX.X%)		XX XX (XX.X%) XX (XX.X%) XX (XX.X%)
Reasons for temporary discontinuations	N Missing data Adverse event Patient's choice Doctor's choice Other	XX XX XX (XX.X%) XX (XX.X%) XX (XX.X%)	XX XX XX (XX.X%) XX (XX.X%) XX (XX.X%) XX (XX.X%)	XX XX XX (XX.X%) XX (XX.X%) XX (XX.X%) XX (XX.X%)
Duration of temporary discontinuations (days)	N Missing data	XX XX	NA	XX XX
	Mean (SD)	XX.XX (X.XX)		XX.XX (X.XX)
	Median	XX.X		XX.X
	[Min; Max]	[XX.X; XX.X]		[XX.X; XX.X]
	[Q1; Q3]	[XX.X; XX.X]		[XX.X; XX.X]

For chemotherapies, interferons and somatostatin analogs, a difference of more than 7 consecutive days is deemed to be a temporary discontinuation.

Programmer note:

- For the variables "Time to first temporary discontinuation", N=number of patients with at least one temporary discontinuation.

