- For the variables "Reasons for temporary discontinuations" and "Duration of temporary discontinuations", N=number of temporary discontinuations.

Table 14.3.1.6: Temporary Discontinuations of the Main Treatment Received at Least Once During the Study – Safety Analysis Set

		Targeted therapies (N=XX)	Other treatments (N=XX)	Total (N=XX)
At least one temporary discontinuation	N	XX	XX	XX
At least one temporary discontinuation	Missing data	XX	XX	XX
	Yes	XX (XX.X%)	XX (XX.X%)	XX (XX.X%)
	No	,	,	,
	NO	XX (XX.X%)	XX (XX.X%)	XX (XX.X%)
Number of temporary discontinuations per patient	N	XX	XX	XX
	Missing data	XX	XX	XX
	Mean (SD)	XX.XX (X.XX)	XX.XX (X.XX)	XX.XX (X.XX)
	Median	XX.X	XX.X	XX.X
	[Min; Max]	[XX.X; XX.X]	[XX.X; XX.X]	[XX.X; XX.X]
	[Q1; Q3]	[XX.X; XX.X]	[XX.X; XX.X]	[XX.X; XX.X]
Reasons for temporary discontinuations	N	XX	XX	XX
1 3	Missing data	XX	XX	XX
	Adverse event	XX (XX.X%)	XX (XX.X%)	XX (XX.X%)
	Patient's choice	XX (XX.X%)	XX (XX.X%)	XX (XX.X%)
	Doctor's choice	XX (XX.X%)	XX (XX.X%)	XX (XX.X%)
	Other	XX (XX.X%)	XX (XX.X%)	XX (XX.X%)
Duration of temporary discontinuations (days)	N	XX	NA	XX
2 station of temporary discontinuations (days)	Missing data	XX	1.11	XX
	Mean (SD)	XX.XX (X.XX)		XX.XX (X.XX)
	Median	XX.X		XX.X
	[Min; Max]	[XX.X; XX.X]		[XX.X; XX.X]
	[Q1; Q3]	[XX.X; XX.X]		[XX.X; XX.X]

The temporary discontinuations were not recorded for patients on "Other" treatments shown in the "Other treatments" column.

Table 14.3.1.7: Permanent Discontinuations of the Treatment at Inclusion Documented in the Study – Safety Analysis Set

		Targeted therapies (N=XX)	Other treatments (N=XX)	Total (N=XX)
Permanent discontinuation	N Missing data Yes No	XX XX XX (XX.X%) XX (XX.X%)	XX XX XX (XX.X%) XX (XX.X%)	XX XX XX (XX.X%) XX (XX.X%)
Time to permanent discontinuation since inclusion (months)	N Missing data Mean (SD) Median [Min; Max] [Q1; Q3]	XX XX.XX (X.XX) XX.X [XX.X; XX.X] [XX.X; XX.X]	XX XX XX.XX (X.XX) XX.X [XX.X; XX.X] [XX.X; XX.X]	XX XX.XX (X.XX) XX.X [XX.X; XX.X] [XX.X; XX.X]

Table 14.3.1.7: Permanent Discontinuations of the Treatment at Inclusion Documented in the Study – Safety Analysis Set

		Targeted therapies (N=XX)	Other treatments (N=XX)	Total (N=XX)
Time to permanent discontinuation since inclusion (N(%))	N Missing data]0-1] months]1-2] months]2-3] months	XX XX XX (XX.X%) XX (XX.X%) XX (XX.X%)	XX XX XX (XX.X%) XX (XX.X%) XX (XX.X%)	XX XX XX XX (XX.X%) XX (XX.X%) XX (XX.X%)

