Time to permanent discontinuation since inclusion (months) – incident patients	 N	XX	XX	XX
medent patients	Missing data Mean (SD) Median [Min; Max] [Q1; Q3]	XX XX.XX (X.XX) XX.X [XX.X; XX.X] [XX.X; XX.X]	XX XX.XX (X.XX) XX.X [XX.X; XX.X] [XX.X; XX.X]	XX XX.XX (X.XX) XX.X [XX.X; XX.X] [XX.X; XX.X]
Time to permanent discontinuation since inclusion (N(%)) –	N	XX	XX	XX
incident patients	Missing data [0-1] months [1-2] months [2-3] months	XX XX (XX.X%) XX (XX.X%) XX (XX.X%)	XX XX (XX.X%) XX (XX.X%) XX (XX.X%)	XX XX (XX.X%) XX (XX.X%) XX (XX.X%)
Time to permanent discontinuation since inclusion (months) –	N	XX	XX	XX
prevalent patients	Mean (SD) Mean [Min; Max]	XX.XX (X.XX) XX.X [XX.X; XX.X]	XX.XX (X.XX) XX.X [XX.X; XX.X]	XX.XX (X.XX) XX.X [XX.X; XX.X]
Time until permanent discontinuation from inclusion $(N(\%))$ – prevalent patients	N	XX	XX	XX
prevalent patients	Missing data [0-1] months [1-2] months [2-3] months	XX XX (XX.X%) XX (XX.X%) XX (XX.X%)	XX XX (XX.X%) XX (XX.X%) XX (XX.X%)	XX XX (XX.X%) XX (XX.X%) XX (XX.X%)
Time until permanent discontinuation from initiation (months)	N Missing data Mean (SD) Mean [Min; Max]	XX XX XX.XX (X.XX) XX.X [XX.X; XX.X]	XX XX XX.XX (X.XX) XX.X [XX.X; XX.X]	XX XX XX.XX (X.XX) XX.X [XX.X; XX.X]
	[Q1; Q3]	[XX.X; XX.X]	[XX.X; XX.X]	[XX.X; XX.X]
Time until permanent discontinuation from initiation (N(%))	N Missing data]0-3] months]3-6] months]6-12] months]12-24] months >24 months	XX XX XX (XX.X%) XX (XX.X%) XX (XX.X%) XX (XX.X%)	XX XX XX (XX.X%) XX (XX.X%) XX (XX.X%) XX (XX.X%)	XX XX XX (XX.X%) XX (XX.X%) XX (XX.X%) XX (XX.X%)
Time until permanent discontinuation from initiation (months)	N	XX	XX	XX
– incident patients	Missing data Mean (SD) Mean [Min; Max] [Q1; Q3]	XX XX.XX (X.XX) XX.X [XX.X; XX.X] [XX.X; XX.X]	XX XX.XX (X.XX) XX.X [XX.X; XX.X] [XX.X; XX.X]	XX XX.XX (X.XX) XX.X [XX.X; XX.X] [XX.X; XX.X]

Table 14.3.1.7: Permanent Discontinuations of the Treatment at Inclusion Documented in the Study – Safety Analysis Set

		Targeted therapies (N=XX)	Other treatments (N=XX)	Total (N=XX)
Time until permanent discontinuation from initiation $(N(\%))$ – incident patients	N	XX	XX	XX
mercent patients	Missing data]0-3] months]3-6] months]6-12] months]12-24] months >24 months 	XX XX (XX.X%) XX (XX.X%) XX (XX.X%) XX (XX.X%)	XX XX (XX.X%) XX (XX.X%) XX (XX.X%) XX (XX.X%) XX (XX.X%)	XX XX (XX.X%) XX (XX.X%) XX (XX.X%) XX (XX.X%) XX (XX.X%)
Time until permanent discontinuation from initiation (months) – prevalent patients	N	XX	XX	XX

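### Time to permanent discontinuation is summarised only in patients who stopped; those still on treatment are omitted rather than censored

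*SAP*

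**What the plan says.** SAP 5.7.1 lists, for each analysis group and each treatment, "Time until permanent discontinuation from inclusion into the study", for incident, prevalent and all patients. The next bullet but one line repeats the same origin in slightly different words. Table 14.3.1.7 suggests the repeat was meant to be time from initiation, because the template has one set of rows starting "Time to permanent discontinuation since inclusion (months" and another starting "Time until permanent discontinuation from initiation (months".

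SAP 4.7 defines the variable as ("Date of final discontinuation – Date of inclusion + 1)/30.4375". SAP 4.5 says of dates: "If the date is completely missing, it will not be replaced". The continuous rows of Table 14.3.1.7 contain N, missing, mean (SD), median, range and, in most blocks, quartiles. They contain no number at risk, censoring count or confidence interval. For first temporary discontinuation, the programmer note to Table 14.3.1.5 states the restriction outright: "N=number of patients with at least one temporary discontinuation".

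Kaplan-Meier is named for two endpoints only: "Overall survival and progression-free survival data will be described by Kaplan Meier curves" (SAP 4.1). For those two, SAP 5.5.1 and 6.1.3 also handle left truncation, so that prevalent patients contribute only from inclusion onward.

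**The concern.** A patient still taking the treatment at the last visit has no final discontinuation date, so the SAP 4.7 formula gives no value and nothing is substituted. The rows therefore describe how quickly the stoppers stopped, not how long patients stay on treatment. The longer a treatment is kept, the more of its patients disappear from its own summary.

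The rows are produced by group and by treatment, so targeted therapies will be read beside other treatments. A treatment kept for years and one stopped at about a year could show similar figures.

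For prevalent patients timed from initiation there is a second problem: they had to be still on treatment at inclusion to be enrolled, so early stoppers are missing. The SAP recognises this for PFS and OS but makes no provision for it here.

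**Working it through.** The documents give no expected duration, stopping rate or number of stops, so there is no planned figure to reproduce. The distributions below are assumptions.

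**Inputs.** Follow-up window W = 24 months from inclusion (SAP 3.3). SAP 5.5.1 says visits after two years are also used, so W = 30 is a sensitivity case. Time on treatment is taken as exponential with true median m and rate λ = ln 2 / m.

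**Formulas.** Share stopped within the window: F = 1 − exp(−λW). Median among stoppers: −ln(1 − F/2)/λ. Mean exposure when the last visit is taken as the stop: F/λ. True mean: 1/λ.

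**Worked case, m = 11, W = 24.** λ = 0.6931/11 = 0.0630. F = 1 − 2^(−24/11) = 0.780. Median among stoppers = −ln(1 − 0.390)/0.0630 = 0.494/0.0630 = 7.8 months.

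**Worked case, m = 24, W = 24.** F = 0.500. Median among stoppers = −ln(0.75) × 24/0.6931 = 0.2877 × 34.62 = 10.0 months.

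| True median (months) | Stopped by 24 months | Median among stoppers |
|---|---|---|
| 11 | 78% | 7.8 |
| 16 | 65% | 9.0 |
| 24 | 50% | 10.0 |
| 36 | 37% | 10.6 |

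A true contrast of 11 against 24 (13 months) reads 7.84 against 9.96 (2.1 months).

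**Sensitivity, true medians 12 against 24.**
- Exponential, W = 24: 8.1 against 10.0.
- Exponential, W = 30: 9.2 against 11.9.
- Weibull shape 0.7, W = 24 (simulated): 5.7 against 6.8.
- Weibull shape 1.5, W = 24 (simulated): 10.4 against 13.4.

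All are too low, with the contrast shrunk.

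**A case where the order reverses (simulated).** Group A: Weibull shape 2, median 9. Group B: one third early stops (exponential, median 3) and two thirds long stayers (exponential, median 60). True medians are 9.0 and 25.1; medians among stoppers are 9.0 and 4.4.

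**Prevalent patients timed from initiation (simulated).** Start dates are uniform over a look-back before inclusion. Patients must be on treatment at inclusion and are followed for 24 months. Median from initiation among stoppers:

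| Look-back (months) | True median 11 | True median 24 |
|---|---|---|
| 6 | 10.7 | 12.9 |
| 12 | 13.5 | 15.8 |
| 24 | 17.6 | 21.1 |
| 36 | 19.6 | 24.8 |

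The bias can be downward or upward. Incident patients have only the downward bias, so the all-patients row mixes the two.

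**What Kaplan-Meier would target from inclusion.** The proportion still on treatment at 12 months is 2^(−12/11) = 47% for m = 11 and 2^(−12/24) = 71% for m = 24. At 24 months it is 22% and 50%.

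**The case against.** Several points on the other side stand.

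- **The primary safety objective is not built on this row.** Protocol 3.1 and 8.3.2.1 name discontinuations, their reasons and adverse events, and the stated estimate is the proportion stopping for intolerance. A reader might infer that the primary safety measure is compromised; the documents do not support that. Proportions and reasons are reported separately and do not depend on the time summary.
- **Patients still on treatment are not invisible.** Table 14.3.1.7 shows how many stopped, with counts by month to 12 months and then every three months to 24. Apart from losses to follow-up, a reader could rebuild approximate cumulative proportions. Total exposure includes continuing patients, but takes the last visit as their last dose: at a true median of 24 its mean is 0.50 × 34.6 = 17.3 months against a true 34.6. These outputs make the bias detectable. They do not correct the mean and median.
- **No test is planned on these rows**, and both documents call strict group comparison inappropriate. The harm is to interpretation, not to error rates.
- **Tempting general statements go too far.** It is not true that every duration is understated, that group differences must shrink, or that the stoppers' median stays below 12 months. The last needs a constant hazard and a hard 24-month window; with 30 months a true median of 36 reads 12.9. A constant hazard is also doubtful for some other treatments, since the CRF offers scheduled stop and cumulative dose reached as stop reasons.
- **Temporary discontinuation cannot be treated alike in all groups.** For chemotherapy, interferon and somatostatin analogues the CRF records whether treatment was postponed and why, without a date, and Table 14.3.1.5 shows NA for other treatments.

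**Conclusion.** The point holds for time to permanent discontinuation. The formula, the missing-date rule and the template together restrict the summary to patients who stopped. That understates time from inclusion whenever some patients remain on treatment. The direction needs no distributional assumption; the size does. Under exponential durations and 24 months, 11 reads 7.8 and 24 reads 10.0. Contrasts between groups are unreliable: shrunk in the common shapes tried, reversed in an early-toxicity mixture.

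For prevalent patients timed from initiation the distortion is real but its direction is not fixed. It depends on a look-back the documents do not give.

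This is a worthwhile correction to a supporting descriptive safety row. It is not a flaw in the primary safety measure.

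**What to change.** In SAP 5.7.1 and Table 14.3.1.7, with a matching definition in SAP 4.7:

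- Estimate time to permanent discontinuation by Kaplan-Meier. Censor patients still on treatment at their last visit and patients lost to follow-up at last contact. Count death on treatment as an event, or state another rule. The rule must be explicit because the template lists both death and loss to follow-up as reasons for permanent discontinuation.
- For time from initiation, use delayed entry at inclusion, as for PFS and OS, and correct the duplicated bullet in 5.7.1.
- Report the median and the 12- and 24-month rates with 95% confidence intervals. The rates remain useful if the median is not reached.
- Label any mean or quartile rows that are kept 'among patients who stopped'.
- For first temporary discontinuation, limit any time-to-event analysis to targeted therapies, where interruption dates are collected, with permanent stop and death as competing events. Otherwise label the row 'among patients with an interruption'.

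Cost: no new data. Treatment start and stop dates are among the key eCRF variables in SAP section 8, and the left-truncation code is already planned. The small downside is that event and censoring rules must be specified, which should be done before the tables are run.

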5.7.2. Adverse Events

The numbers and percentages of patients with the following characteristics will be shown overall, and by group at inclusion during the study (targeted therapy/other treatments). We will also show the results by treatment being received at the time of inclusion and during the study: everolimus/sunitinib/chemotherapy/somatostatin analogs etc.

- at least one adverse event,
- at least one serious adverse event,
- at least one adverse event with a suspected relationship with the study treatment,
- an adverse event which was fatal,
- at least one adverse event resulting in permanent discontinuation of treatment,
- at least one adverse event resulting in dosage adjustment/temporary discontinuation of treatment.

- at least one adverse event with a suspected relationship with the study treatment leading to permanent discontinuation of the treatment,
- at least one adverse event with a suspected relationship with the study treatment leading to a dosage adjustment/temporary discontinuation of treatment,
- at least one serious adverse event with a suspected relationship with the study treatment leading to permanent discontinuation of the treatment,
- at least one serious adverse event with a suspected relationship with the study treatment leading to a dosage adjustment/temporary discontinuation of treatment.

The same information will be produced for grade ≥ 3 adverse events.

The following information will also be shown:

- at least one grade 3 adverse event,
- at least one grade 3 serious adverse event,
- at least one grade 3 adverse event with a suspected relationship with the study treatment,
- at least serious grade 3 adverse event with a suspected relationship with the study treatment,
- at least one grade 4 or higher adverse event,
- at least one grade 4 or higher adverse event with a suspected relationship with the study treatment.

The adverse events will also be described by treatment group, in patients who received treatment at least once during the study (targeted therapies/other treatments; the other treatments will also be described depending on whether these involved chemotherapy/somatostatin analogs/others) by System Organ Class (SOC) and Preferred Term (PT). The same analysis will be presented for adverse events with a suspected relationship with the study treatment, grade 3 adverse events with a suspected relationship with the study treatment, serious grade 3 adverse events with a suspected relationship with the study treatment, adverse events grade =3, adverse events ≥4, for serious adverse events, non-serious adverse events, serious grade =3 adverse events, adverse events which resulted in temporary discontinuation of treatment, adverse events which resulted in permanent discontinuation of treatment and adverse events which resulted in the death of patient.

In terms of the analysis by treatment received during the study, several rules have been defined:

The denominator will be the number of patients who received the ongoing treatment during the prospective period at least once. In the case of combination treatments, the treatments will be separated and the patient will be counted several times.

The AE will be deemed to be on treatment until 28 days after the treatment is stopped. Similarly, if the investigator links an AE to a treatment, this will also be counted on this related treatment (regardless of the dates the treatment is taken).

If the treatment is still ongoing at the time of last news, the AE will be deemed to be on treatment for up to 28 days after the date of last news.

Amongst the "other" treatments, Lutathera treatment will be deemed to be metabolic radiotherapy.

If the date of onset of the adverse event is missing:

- If the day of the event is missing, the event will be attributed to all treatments received during the month when the AE was declared.
- if the day and month of the event are missing, the event will be attributed to all treatments during the year in which the AE is declared unless the treatment was received after the end of the AE.

For combination treatments, the start and end date of the combination were not recorded in the CRF. The visit immediately before the report of the additional combination will therefore be deemed to be the start date and the visit corresponding to discontinuation of the combination will be deemed to be the end date of the combination, unless the combination began or finished during a treatment line (where start and end dates are reported). The 28-day rule also applies to combination treatments.

The AEs will be analysed as follows:

	Actual exposure	Actual exposure +28 days	Treatment reported in the "Causality with the study treatment" column
At least one adverse event		X	
At least one serious adverse event		X	
At least one adverse event with a suspected relationship with the study treatment			X
At least one adverse event resulting in death		X	
At least one adverse event leading to permanent discontinuation of treatment	X		
At least one adverse event leading to change in dosage/temporary discontinuation of treatment	X		
At least one adverse event with a suspected relationship with the study treatment leading to permanent discontinuation of treatment	X		X
At least one adverse event with a suspected relationship with the study treatment leading to adjustment of dosage/temporary discontinuation of treatment	X		X
At least one adverse event with a suspected relationship with the study treatment leading to temporary discontinuation of treatment	X		X
At least one serious adverse event with a suspected relationship with the study treatment leading to permanent discontinuation of treatment	X		X
At least one serious adverse event grave with a suspected relationship with the study treatment leading to adjustment of dosage/temporary discontinuation of treatment	X		X
At least one serious adverse event with a suspected relationship with the study treatment leading to temporary discontinuation of treatment	X		X

^{*} AEs on treatment analysed as reported in the actual exposure and in the "causality with the study treatment" column.

Adverse events will be listed overall, together with the grade ≥ 3 adverse events, serious adverse events, adverse events with a suspected relationship to the study treatment leading to permanent discontinuation of the treatment and adverse events with a suspected relationship to the study treatment leading to temporary discontinuation of the treatment.

NB: the listings will show the retrospective adverse events and the prospective adverse events, whereas the summary tables will only include the prospective adverse events.

The listing of adverse events reported in patients excluded from the safety analysis set will be provided where applicable.

Handling of missing data:

If the seriousness (serious/non-serious) and/or causality with the treatment are missing, the most adverse situation for treatment is assumed in the summary tables, i.e. a serious case and/or one related to the study treatment.

